## 7.2 PATIENT DISCONTINUATION FROM THE STUDY

Patients will be discontinued from the study in the cases of patient death or lost to follow-up.

Patients may decide to discontinue participation in the study; any such patient withdrawing from the study will be asked to complete the Early Termination Visit assessments. The reason for patient discontinuation from the study will be recorded on the eCRF. No patients who discontinue from the study will be replaced under any circumstances.

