In all of these circumstances, patients should continue to attend all remaining study visits and undergo all scheduled testing.

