3.3 Schedule of Evaluations and Analysis Visit Windows

The schedule of visits and procedures are provided in the study protocol, LL-BMT10001, version 1.2, section 1.3. The study consists of a screening period, 2 acclimation periods where the subject wears 2 sets of nonmedicated lens for 1 week each, 1 treatment week where the subject wears 1 set of LL-BMT1

lenses for 1 week, and a follow-up visit after lens removal. Visit days and windows are summarized in the table below:

Visit	Target Day of the Visit	Visit Windows (Days) for Analyses
Visit 1 - Screening	-45 to -14	< -14
Visit 2 – Acclimation	-14	-14
Visit 3 – Acclimation	-7	-7
Visit 4 – Acclimation	-6	-6
Visit 5 – Baseline	0	0
Visit 6 – LL-BMT1 Lens Insertion	1	1
Visit 7 – On-treatment	4	4
Visit 8 – End of treatment	7	7
Visit 9 – Follow-up	8	8
Visit 10 – Conditional Follow-up / End of study	9	9

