6.3 Missing Data and Imputation

No Imputation will be conducted for this study.

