6.8 Secondary Analysis

There will be both safety and efficacy assessments in the secondary analysis.

The secondary safety analysis will consist of identifying the following:

- Percent of patients with ≥ 5 mmHg increase from baseline in IOP at each visit
- “Abnormal” and “Severe” slit-lamp biomicroscopy findings at the Baseline, Day 1, and Day 7 Visits
- Contact lens protein deposits at the Day 7 Visit
- Change from Baseline in CLDEQ-8 results at the Day 7 Visit

The secondary efficacy analysis will consist of identifying the change from baseline in IOP at each visit. Study eyes only within the modified intent-to-treat population will be used for this part of the analysis.

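### A study withdrawer's CLDEQ-8 score and any early stopper's lens deposits have no place in the Day 7-only tolerability summaries

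*Protocol*

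**What the plan says.** Tolerability is a stated objective (Protocol 1.1 and 3, SAP 2.2). SAP 6.8 lists two measures of it, each at a single time point: "Contact lens protein deposits at the Day 7 Visit" and "Change from Baseline in CLDEQ-8 results at the Day 7 Visit". Protocol 9.4.2 has the same two.

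A patient can leave treatment early by two routes.

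- **Stops LL-BMT1, stays in the study.** Protocol 7.1 lists the reasons and then says that "patients should continue to attend all remaining study visits and undergo all scheduled testing". Protocol 6.5.1 also keeps a patient with a large IOP rise in the study after the lens is removed.
- **Withdraws from the study.** Protocol 7.2 says that "any such patient withdrawing from the study will be asked to complete the Early Termination Visit assessments". In the Schedule of Activities (Protocol 1.3), the Early Termination column marks lens removal, biomicroscopy and CLDEQ-8. It does not mark the CL assessment, the row that contains deposits, which is marked only at Day 1 and Day 7.

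On the analysis side, SAP 3.3 announces that "Visit days and windows are summarized in the table below". The row "Visit 8 – End of treatment" has Day 7 as both target and window, and the table has no Early Termination row. SAP 6.3 adds: "No Imputation will be conducted for this study".

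**The concern.** A patient who gives up the lens early may be the most informative one for tolerability, and the two endpoints meant to describe it look past that patient. The withdrawer fills in a CLDEQ-8 that the SAP does not use. The withdrawer's lens may be in the investigator's hand, but nobody is asked to grade it. The patient who stops but stays has no worn lens at Day 7, and nothing asks for the lens to be graded on the day it came out.

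If the reason for stopping was discomfort or a fouled lens, the reported deposits describe only patients who wore the lens for the full week. The reported CLDEQ-8 change leaves out anyone who withdrew. Five patients are dosed and none is replaced (Protocol 5.5 and 7.2), so one such patient is a fifth of the data.

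**Working it through.** **1. Which data reach which summary** (Protocol 1.3, 7.1 and 7.2; SAP 3.3, 6.3 and 6.8)

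| Patient | CLDEQ-8 collected | CLDEQ-8 in the Day 7 summary | Deposits graded after wear | Deposits in the Day 7 summary |
|---|---|---|---|---|
| Completes 7 days | Day 7 | Yes | Day 7 | Yes |
| Stops lens, stays in study | Day 7, days after removal | Yes | Not scheduled at removal; no worn lens at Day 7 | No |
| Withdraws before Day 7 | Early Termination Visit | No | Not scheduled | No |

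Three cells fall out: the withdrawer's CLDEQ-8 and both early stoppers' deposits. The CLDEQ-8 of a patient who stays does not fall out.

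**2. The plan's drop-out allowance** (Protocol 9.2, SAP 3.1)

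The plan wants 5 evaluable patients and assumes 10% to 20% drop-out.

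- 5 / (1 − 0.10) = 5.56, rounded up to 6.
- 5 / (1 − 0.20) = 6.25, rounded up to 7.

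This reproduces the stated maximum of 7. Those 7 are the patients who start acclimation. Only 5 are dosed, so the allowance is used up before the first LL-BMT1 lens goes in.

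The documents give no drop-out rate after insertion. If the same 10% to 20% applied then (an assumption), the chance that at least one of five is lost would be:

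- 1 − 0.90^5 = 0.41
- 1 − 0.80^5 = 0.67

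The rate could well be lower, since everyone dosed has already passed two weeks of lens wear.

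**3. Effect on the mean CLDEQ-8 change, withdrawers only**

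The scores are assumed. Four completers change by +2 and one withdrawer by x at Early Termination. With the value used, the mean is (4 × 2 + x) / 5. Without it, the mean is (4 × 2) / 4 = 2.0. The difference is (x − 2) / 5.

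| Withdrawer's change x | Mean, value used (n = 5) | Mean, Day 7 only (n = 4) | Difference |
|---|---|---|---|
| +5 | 2.6 | 2.0 | 0.6 |
| +10 | 3.6 | 2.0 | 1.6 |
| +15 | 4.6 | 2.0 | 2.6 |
| +25 | 6.6 | 2.0 | 4.6 |

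All these changes are possible. The printed form runs from 1 to 37 (maximum 4+5+4+5+4+5+4+6), and inclusion criterion 8 caps the baseline score at 11.

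**4. Effect on deposits, either route**

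Suppose the early stopper's lenses carried deposits and the four completers' did not (again assumed). Day 7 grading gives 0/4 = 0%. Grading at removal would give 1/5 = 20%.

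**The case against.** The strongest reply is that early stoppers do not vanish from the trial, and this stands. The primary AE rate uses everyone with lenses inserted (SAP 4.2 and 6.7). A patient who chooses to stop must be asked about AEs (Protocol 7.1). Clinically significant abnormal findings become AEs, and extra examinations are allowed (Protocol 8.2). The reason for leaving the study is recorded (Protocol 7.2), disposition is summarised and listed (SAP 6.1), and line listings are promised for each patient (Protocol 9.4.7). With five patients and no hypothesis test, an Early Termination score should be visible in a listing. None of this grades the lens or brings that score into the endpoint summary.

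Three stronger readings are tempting, and the documents do not support them.

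- *All poor tolerators drop out of the CLDEQ-8 result.* They do not. Under Protocol 7.1 a patient who stops but stays attends Day 7, and that score is summarised.
- *Waiting until Day 7 dilutes the score because the form asks about the past two weeks.* Take a patient who stops on Day 2. At Day 7 the 14 recall days are Day −6 to Day 7, with LL-BMT1 worn on Days 1 and 2, so 2 of 14. At removal on Day 2 they are Day −11 to Day 2, again 2 of 14. The mismatch between two-week recall and one-week wear affects completers too. Several items also ask only about time wearing lenses.
- *The bias always favours the product.* Lens damage, sponsor decision, pregnancy (Protocol 7.1), IOP elevation (6.5.1) and respiratory symptoms (10.2) can all end wear without discomfort. Losing a comfortable patient would bias the summary the other way.

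It is also fair to say that pooling a lens worn two days with lenses worn seven mixes exposures and could lower the deposit frequency. The fix has to allow for that.

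**Conclusion.** The point holds in a limited form. As written, a withdrawer's CLDEQ-8 enters no planned summary, and no early stopper's lens is graded for deposits. When the reason for stopping is poor tolerability, the deposit summary (both routes) and the CLDEQ-8 summary (withdrawers only) look better than they should.

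Each such patient is 1 of 5 (20%). Under the assumed scores, one withdrawer at +10 moves the mean change from 2.0 to 3.6. The size depends entirely on the assumed score, and nothing is lost if all five complete seven days.

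The primary AE rate, disposition and listings are unaffected, and both endpoints are descriptive. The change is still worth making: tolerability is an objective, five patients leave no slack, and the remedy is very cheap.

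**What to change.** **Protocol 1.3.** Add an X for CL assessment in the Early Termination column. Add a footnote: when LL-BMT1 is permanently removed at a site visit before Day 7, CLDEQ-8 and the CL assessment of the removed lens are done at that visit. This reaches patients who stop but stay, whom the Early Termination Visit does not cover.

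**SAP 3.3 and 6.8.** Define the end-of-treatment value for CLDEQ-8 and deposits as the value at permanent lens removal, on Day 7 or earlier. Summarise it in all dosed patients, beside the Day 7-only summary, with the denominator shown for each. List wear time and reason for stopping for every patient.

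**Cost.** One X, one footnote and a short SAP definition. The assessments take minutes at a visit where the lens is already coming out, and no treatment rule changes. The small downside is that wear time will differ between patients, so deposits on a short-worn lens must be read with the listed wear time. That is why the Day 7-only summary stays beside the new one.

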## 7.3 LOST TO FOLLOW-UP

A patient will be considered lost to follow-up per Principal Investigator discretion and upon consultation with the Sponsor upon failure to adhere to the protocol.

The following actions must be taken if a patient fails to return to the clinic for a required study visit:

- The site will attempt to contact the patient and reschedule the missed visit on the following day and counsel the patient on the importance of maintaining the assigned visit schedule and ascertain if the patient wishes to and/or should continue in the study.
- Before a patient is deemed lost to follow-up, the investigator or designee will make every effort to regain contact with the patient (where possible, 3 telephone calls and a certified letter to the patient's last known mailing address or local equivalent methods). These contact attempts should be documented in the patient's medical record or study file.

- Should the patient continue to be unreachable, he or she will be considered to have withdrawn from the study with a primary reason of lost to follow-up.

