## 7 STUDY INTERVENTION DISCONTINUATION AND PATIENT DISCONTINUATION

### 7.1 DISCONTINUATION OF STUDY INTERVENTION

Patients may be discontinued from study intervention for any of the following reasons:

- Investigator decision: The investigator can decide that the patient should be discontinued from study intervention for any reason.
- Patient decision: Patients who decide to discontinue study intervention should be explicitly asked about the contribution of possible AEs to their decision, and any AE information elicited should be documented. Preferably the patient should withdraw consent in writing and, if the patient refuses or is physically unavailable, the site should document and sign the reason for the patient's failure to withdraw consent in writing. The patient is lost to follow-up after a reasonable number of attempts to contact the patient (including documented phone calls and/or emails, and a certified letter) have been completed.
- Sponsor decision: The Sponsor or its designee can stop the patient's participation in the study for medical, safety, regulatory, or other reasons consistent with applicable laws, regulations, and GCP guidelines.
- Pregnancy: If a patient becomes pregnant during the study, the patient will be immediately discontinued from study intervention. Only pregnancies considered by the

investigator as related to study drug (e.g., resulting from an interaction between study drug and a contraceptive drug) are considered AEs unto themselves. However, all pregnancies with an estimated conception date that occurred during the study must be recorded in the AE section of the eCRF and investigators must actively follow up, document, and report on the outcome of all pregnancies.

- AE: If the investigator decides that the study intervention should be discontinued because of an AE, the investigational product is to be discontinued and appropriate measures are to be taken. The Sponsor or its designee is to be alerted immediately.
- Damage to both LL-BMT1 lenses: The investigator should take care with lens handling, especially during removal of the lens for IOP assessment. If a lens is damaged during removal, a new lens cannot be inserted in the patient's eye. Patients can remain on the study if at least one LL-BMT1 lens is able to be reinserted in one of the patient's eyes. If both lenses are damaged during removal, then the patient will not be allowed to continue with study procedures.

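### The opening sentence of Protocol 7.3 lets a reachable but non-adherent patient be classed as lost to follow-up, which contradicts the contact-based definition in 7.1 and in the rest of 7.3.

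*Protocol*

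**What the plan says.** Protocol 7.3 opens with a discretionary rule: a patient is "lost to follow-up per Principal Investigator discretion and upon consultation with the Sponsor upon failure to adhere to the protocol". The bullets below it are introduced by "The following actions must be taken if a patient fails to return to the clinic for a required study visit". They then set a different test. One requires contact efforts first: "Before a patient is deemed lost to follow-up, the investigator or designee will make every effort to regain contact with the patient". The last one reads "Should the patient continue to be unreachable, he or she will be considered to have withdrawn from the study", with lost to follow-up as the primary reason.

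Protocol 7.1, in its item on patient decisions, also relies on contact: "The patient is lost to follow-up after a reasonable number of attempts to contact the patient". After listing the reasons for stopping study intervention, 7.1 adds: "In all of these circumstances, patients should continue to attend all remaining study visits and undergo all scheduled testing".

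Protocol 7.2 gives the consequence of the label: "Patients will be discontinued from the study in the cases of patient death or lost to follow-up". Of patients who choose to leave, it says that "any such patient withdrawing from the study will be asked to complete the Early Termination Visit assessments". It also rules out replacement and has the reason for discontinuation entered on the eCRF. Protocol 8.3.4 keeps adverse event recording open for 7 days (non-serious) or 30 days (serious) after participation ends.

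**The concern.** Two tests for the same status stand side by side. One turns on adherence, as judged by the investigator with Sponsor input. The other turns on whether the patient can be reached. A patient can fail the first and pass the second. Protocol 4.1 and 6.1.2 do not let patients take the lenses out themselves (10.2 makes a COVID-19 exception), so a patient who removes a lens at home and then answers the telephone is non-adherent but not lost.

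The status matters because 7.2 attaches the end of study participation to it. Safety is the primary objective and tolerability a secondary one, and failure to keep a continuous-wear lens in place may itself be tolerability information. With up to two sites, two investigators could classify the same patient differently and each could cite the protocol. The patient listing of disposition (SAP 6.1) would then show a reason that does not describe what happened.

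**Working it through.** **Plan's own figure.** The only stated number nearby is the consent target in Protocol 9.2 and SAP 3.1: up to 7 consented to obtain 5 evaluable at 10%–20% dropout. At 10%, 5 / (1 − 0.10) = 5.56, so 6. At 20%, 5 / (1 − 0.20) = 6.25, so 7. The stated 7 reproduces at the upper end and is not in dispute. It gives no reserve after enrolment, because the Schema limits dosing to 5 patients even if all 7 pass acclimation.

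**The passages compared.**

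| Place in Protocol | Test or rule | Must contact have failed? |
|---|---|---|
| 7.3, opening sentence | Non-adherence, investigator discretion, Sponsor consulted | No |
| 7.3, bullets | Missed visit, contact efforts, still unreachable | Yes |
| 7.1, patient decision item | Reasonable contact attempts completed | Yes |
| 7.2 | Label leads to discontinuation from the study | Not addressed |
| 7.1, closing sentence | Off study intervention, all visits and tests continue | Not applicable |

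The bullets do not clearly limit the opening sentence, because they are introduced for missed visits only. A patient who attends but deviates in another way is outside that introduction. The first bullet also has the site consider whether a patient it has reached ought to carry on, so the section does contemplate removing a reachable patient.

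**What would stop.** Under the Schedule of Activities (1.3), a patient labelled after the Day 1 insertion could lose:
- BCVA on Days 4, 7 and 8
- biomicroscopy on Days 4 and 7
- IOP on Days 4, 7 and 8, and on Day 9 if triggered
- CLDEQ-8 on Day 7
- adverse event questioning at each of these visits

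The Early Termination Visit column covers all of these assessments, but 7.2 asks for that visit only when the patient decides to withdraw.

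**What would continue.** Seven days of non-serious adverse event recording after a Day 1 exit reaches Day 8 (1 + 7). After a Day 2 exit it reaches Day 9 (2 + 7), the last possible scheduled visit. Serious events are covered for 30 days. After the final visit this relies on the patient calling the site.

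**Size for one patient.** Inputs: 5 patients, both eyes treated (Protocol 4.1), and a primary rate of 100 × adverse events / eyes exposed (Protocol 9.4.2, SAP 5.1).
- Share of patients: 1 / 5 = 20%.
- Share of eyes: 2 / (5 × 2) = 2 of 10.
- The exposed patient stays in the safety population, so the denominator stays at 10. Each countable ocular event missed lowers the rate by 100 × 1 / 10 = 10 per 100 eyes.
- Nothing fills the gap: no replacement (Protocol 7.2) and no imputation (SAP 6.3).

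**Precision, for illustration.** If no fully observed patient has an event, the exact one-sided 95% upper bound is 1 − 0.05^(1/n). This is 45% for n = 5 and 53% for n = 4. The plan does not propose this calculation.

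**The case against.** The strongest reply is that the literal reading is opposed by text around it. The same section demands contact efforts before the label and ties it to an unreachable patient, and 7.1 uses the same idea. The opening sentence also requires Sponsor consultation, so the investigator does not act alone. All of this stands, and it makes the fault an internal contradiction rather than one unopposed rule.

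A reader might infer that the sentence cuts off safety data from patients who tolerate the lens poorly. The documents do not support that. A patient who removes a painful lens fits most naturally under 7.1, as a patient decision, an adverse event or an investigator decision. For patient decisions, 7.1 requires the site to ask whether adverse events contributed, and its closing sentence keeps these patients in all remaining visits. Data already collected are retained, and recording continues for 7 or 30 days. Selective loss of poor tolerators is conjecture.

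A reader might also construct a case in which two unrecorded events take the rate from 20 to 0 per 100 eyes. That ignores the painful lens, which would itself be a reportable event with onset during treatment, so the rate would not be 0. Moreover, the treatment-emergent definition (Protocol 8.3.1, SAP 6.7) counts onset during treatment. Whether events after lens removal count depends on that definition, not on 7.3.

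Finally, much of the remedy already exists, since patient noncompliance is a protocol deviation under 10.1.10. That is true, but it does not remove a sentence that sends the same patient to a different outcome.

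**Conclusion.** The point holds as a contradiction between the opening sentence of 7.3 and three other places: the 7.3 bullets, the contact-based definition in 7.1, and the rule in 7.1 that visits continue. Its effect is conditional. If the sentence were applied to a reachable patient, scheduled examinations and active questioning would end for 1 of 5 patients (2 of 10 eyes), with no Early Termination Visit stated and the wrong reason recorded. Each ocular event missed would lower the primary rate by 10 per 100 eyes. That figure assumes all five patients receive both lenses and that the missed event would have met the treatment-emergent definition. How often the sentence would be used is not stated and may be never. No endpoint, analysis population or sample-size figure changes. The correction is still worth making in a five-patient, safety-primary study with no replacement and no imputation.

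**What to change.** Reconcile the passages. Delete the clause in the opening sentence of 7.3 that makes non-adherence a trigger, so that lost to follow-up applies only after the documented contact attempts already described in 7.3 have failed. Point 7.1 to that single definition. State that non-adherence is recorded, with its reason, as a protocol deviation under 10.1.10, and that the patient's remaining visits continue in line with the closing sentence of 7.1.

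The cost is one clause deleted in 7.3 and a cross-reference. No new visits, data collection or analyses are needed, and the SAP does not need to change.

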## 8 STUDY ASSESSMENTS AND PROCEDURES

### 8.1 EFFICACY ASSESSMENTS

- **Goldmann applanation tonometry.** Intraocular pressure will be measured with a Goldmann applanation tonometer that is calibrated pre-study and monthly during study participation.

### 8.2 SAFETY AND OTHER ASSESSMENTS

Abnormal findings that are of clinical significance will be recorded as AEs on the eCRFs.

- **Ultrasound pachymetry.** Corneal thickness will be measured using an ultrasound pachymeter.
- **Humphrey visual field assessment.** Visual field (perimetry) will be assessed using a Humphrey Field Analyzer. If Humphrey visual field assessment has been completed within 6 months of Screening Visit, it does not have to be repeated at the Screening Visit
- **Contact Lens (CL) Assessment:** Assessments will include contact lens centration, movement with blinking, and lens surface wettability/deposits, as described in ISO 11980:2012.
- **Heart rate and blood pressure.** Heart rate and blood pressure will be measured by a manual or automated sphygmomanometer.
- **Pregnancy testing.** Pregnancy testing will be performed using a human chorionic gonadotropin pregnancy urine dipstick test on women of childbearing potential.
- **Best-corrected visual acuity.** BCVA will be quantified using the ETDRS visual acuity protocol (at a distance of 3 m) and the number of letters read correctly will be recorded on the eCRF.
- **Biomicroscopy.** Biomicroscopy will be performed by slit-lamp examination of conjunctiva, cornea, and iris with findings reported on a scale of 0 = none, 0.5 = trace, 1 = mild, 2 = moderate, and 3 = severe. The status of the lens will be assessed using the Age-Related Eye Disease Study scale.
- **Goldmann applanation tonometry.** IOP will be measured with a Goldmann applanation tonometer. During the study, the LL-BMT1 contact lens will be removed in order to perform IOP assessment. Of particular significance, all lens insertions and removals will be conducted by the investigator. IOP will be assessed 3 minutes after lens removal, with the goal of reinserting the lens within 5 minutes of removal. Two consecutive IOP measurements of each eye were obtained. If the 2 measurements differed by more than 2 mmHg, a third measurement was obtained. For each eye, IOP was analyzed as the mean

of 2 measurements or as the median of 3 measurements. For each patient, change from baseline IOP was determined by averaging the values for each eye (Sherwood 2006).

- **Conjunctival hyperemia.** The Efron Grading Scales for Contact Lens Complications will be performed using a conjunctival hyperemia scale.

Unscheduled visits can be included if safety concerns arise. Additional examinations may be performed as necessary to ensure the safety and wellbeing of patients during the study. eCRFs should be completed for each unscheduled visit.

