### 2.3 POTENTIAL RISKS AND BENEFITS TO HUMAN PATIENTS

Adverse reactions of greatest concern reported with bimatoprost eyedrops include pigmentation (including blepharal pigmentation and iris hyperpigmentation), eyelash changes, intraocular inflammation, macular edema, and hypersensitivity. In controlled clinical trials, the most common adverse reaction was conjunctival hyperemia (31%). Approximately 1.6% of patients discontinued therapy due to conjunctival hyperemia. Other adverse drug reactions (reported in 1% to 4% of patients) with Lumigan® 0.01% included conjunctival edema, conjunctival hemorrhage, eye irritation, eye pain, eye pruritus, erythema of eyelid, eyelids pruritus, growth of eyelashes, hypertrichosis, instillation site irritation, punctate keratitis, skin hyperpigmentation, vision blurred, and visual acuity reduced. In post-marketing use, AEs reported also include asthma-like symptoms, dizziness, dry eye, dyspnea, eye discharge, eye edema, foreign body sensation, headache, hypersensitivity (including signs and symptoms of eye allergy and allergic dermatitis), lacrimation increased, and periorbital and lid changes (including deepening of the eyelid sulcus; Lumigan PI).

The bimatoprost in LL-BMT1 is printed on Group 4 extended-wear contact lenses. Risks to patients in the present study are those typical of contact lenses.

The potential benefit to patients in this study is the lowering of IOP without the use of daily eyedrops.

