## 9 STATISTICAL CONSIDERATIONS

### 9.1 STATISTICAL HYPOTHESES

There are no formal study hypotheses to be tested in this study. We hypothesize that no safety concerns are revealed in eyes receiving LL-BMT1.

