5.2 Secondary Endpoints

The secondary safety endpoints include the following:

- AEs
- Concomitant medications
- Heart rate and blood pressure
- BCVA
- IOP
- Biomicroscopy
- Conjunctival hyperemia
- Percent of patients with ≥ 5 mmHg increase from baseline in IOP at each visit
- Abnormal slit-lamp biomicroscopy findings at the Baseline, Day 1, and Day 7 Visits
- Contact lens protein deposits at the Day 7 Visit
- Change from Baseline in CLDEQ-8 results at the Day 7 Visit

The secondary efficacy endpoint will be the change from baseline in IOP at each visit.

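### The graded slit-lamp exam omits the anterior chamber, so intraocular inflammation, a risk the protocol ranks among the most worrying, has no baseline grade and no documented absence

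*Protocol*

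**What the plan says.** Protocol Section 2.3 states that the reactions of most concern with bimatoprost eyedrops "include pigmentation (including blepharal pigmentation and iris hyperpigmentation), eyelash changes, intraocular inflammation, macular edema, and hypersensitivity". Wider periorbital and lid changes appear later in the same section, as post-marketing reports only.

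Section 8.2 sets the slit-lamp content: "Biomicroscopy will be performed by slit-lamp examination of conjunctiva, cornea, and iris with findings reported on a scale" that runs 0, 0.5 (trace), 1, 2, 3. It adds: "The status of the lens will be assessed using the Age-Related Eye Disease Study scale". A separate Efron scale covers conjunctival hyperemia.

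SAP 5.2 lists as a secondary safety endpoint "Abnormal slit-lamp biomicroscopy findings at the Baseline, Day 1, and Day 7 Visits". SAP 6.8 uses the same three visits. Neither section lists the structures to be summarised.

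Protocol Section 9.1 says there is no formal hypothesis and then adds: "We hypothesize that no safety concerns are revealed in eyes receiving LL-BMT1". Section 4.1 describes the main aim as a full descriptive account of the safety endpoints.

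**The concern.** The risk section and the examination section do not match. Intraocular inflammation is named as a leading risk, yet the anterior chamber, where a slit lamp would show cells and flare, is not among the structures to be graded. Lids and lashes are also missing.

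This is a five-patient, open-label study without a control arm, so a complete description is most of what it can offer on safety. If the slit-lamp table shows nothing abnormal, a reader may take that as evidence against intraocular inflammation. On the plan as written, the table carries no such evidence, because the anterior chamber was never a graded row. A cell or flare finding first noticed on Day 4 or Day 7 would also have no graded pre-treatment value to compare it with.

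**Working it through.** The plan gives no figure on this point to reproduce. The check is a comparison of sections and a count of examinations.

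**1. Named reactions against graded structures.** Taking cells and flare as the usual slit-lamp signs of anterior chamber inflammation:

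| Reaction in Protocol 2.3 | Graded item in 8.2 |
|---|---|
| Iris hyperpigmentation | Iris is graded; the type of finding is not specified |
| Blepharal pigmentation | None (lids not listed) |
| Eyelash changes | None (lashes not listed) |
| Intraocular inflammation | None for the anterior chamber; inflammatory iris findings are neither named nor excluded |
| Macular edema | None; BCVA is indirect |
| Hypersensitivity | Conjunctival signs only |

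No other part of the protocol or SAP fills the gap. Section 8.3.8 names no events of special interest. Section 10.1.9.1 mentions biomicroscopy and ophthalmoscopy results only as content of the medical record.

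**2. Examinations affected.** The Schedule of Activities (Section 1.3) has biomicroscopy at Visits 1 to 8.
- Before the medicated lens: Visits 1 to 5, plus Visit 6 (Day 1), where Section 1.2 and footnote d of Section 1.3 put the exam before insertion. That is 6.
- On treatment: 8 − 6 = 2 (Day 4 and Day 7).
- After lens removal: none on Day 8 or Day 9. The Early Termination Visit does include biomicroscopy.
- Eyes: 5 patients × 2 = 10. On-treatment eye-examinations: 10 × 2 = 20.
- The SAP endpoint uses Baseline, Day 1 and Day 7, so only 1 of its 3 time points is on treatment.

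**3. What the adverse event route still captures.**
- Section 8.2 opens by requiring clinically significant abnormal findings to be recorded as AEs.
- Section 8.3.1 counts an unintended sign as an AE. No symptom is needed.
- Section 8.3.4 starts each post-Baseline visit with an open question, followed by directed questioning and examination where judged appropriate.
- Section 8.2 closes by allowing additional examinations.

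A clinically significant anterior chamber sign, once seen, is therefore recorded. Three things are not: a trace or mild finding judged not clinically significant, a baseline grade, and a record that the chamber was examined and was clear.

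**4. What a graded absence would be worth.** If all 5 patients were graded clear, the one-sided 95% upper limit for the event rate would be 1 − 0.05^(1/5) = 0.451, or about 45%. The gain is descriptive. It would not establish that the event is rare.

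**The case against.** A reader might infer that inflammation and lid reactions would go unrecorded unless the patient complained. The documents do not support that. Sections 8.2 and 8.3.1 make a clinically significant sign reportable without symptoms, and Sections 8.2 and 8.3.4 allow further examination. The primary endpoint is the AE rate, which would include such events.

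A reader might also count all eight slit-lamp exams as lost on-treatment information. Six precede the drug. Nor is the absence of safety concerns the trial's conclusion: Section 9.1 states it as an informal hypothesis.

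Further points against:
- Section 8.2 does not say which iris findings are graded, so inflammatory iris signs might be captured. It cannot be said that intraocular inflammation has no coverage at all.
- The eCRF is not in the documents and may contain fields that Section 8.2 does not list.
- The Section 2.3 list concerns eyedrops. Here wear lasts 7 days, and Section 4.3 gives about 26 µg released against about 105 µg from drops (26/105 = 25%). Nothing shows that pigmentation or lash change could appear in that time. The only lid item on the leading list is blepharal pigmentation.

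These points narrow the concern, and the last makes the lid and lash part weak. They leave the anterior chamber gap open. The AE route depends on judgement, has a significance threshold well above trace, and never documents absence. The lower amount released does not settle the matter either, since Section 4.3 itself expects greater bioavailability than with drops.

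**Conclusion.** The concern holds in a limited form. Anterior chamber inflammation, a risk the protocol ranks among the most important, is not systematically looked for or graded and has no baseline grade. What is missing is trace or mild findings and documented absence, at two scheduled on-treatment exams (up to 20 eye-examinations), of which the SAP summary would show only Day 7. Clinically significant signs remain reportable, and the primary endpoint's definition is unaffected.

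This assumes that sites grade what Section 8.2 lists, that the eCRF follows it, and that both eyes of all five patients are examined. The lid and lash gap is real on paper but of lower priority. The change is worth making because it costs little and ungraded observations cannot be recovered at analysis.

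**What to change.** - **Protocol 8.2:** add anterior chamber cells and flare as graded items, for example on the scale already used for the other structures, at visits that already have biomicroscopy. The minimum is Baseline, Day 4, Day 7 and Early Termination.
- **SAP 5.2 and 6.8:** name the structures summarised and add rows for cells and flare. Show the Baseline grade beside the on-treatment grades, and include Day 4.
- **Optional, lower priority:** treat lids and lashes in the same way.
- **If the examination is not changed, or the data are already collected:** state in the SAP and report that these risks were captured only through AE reporting, and that an unremarkable slit-lamp table does not document a clear anterior chamber.

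The cost is a few more eCRF fields, slightly longer exams, a few table rows, and an amendment with the IRB approval that the Statement of Compliance requires. No new visit or instrument is needed.
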